cMRI	cardiac magnetic resonance imaging

KEYWORDS

- COVID-19
- Heart failure
- Ejection fraction
- Machine learning

STUDY SUMMARY

TITLE DUO-EF-19: Diagnosis of Heart Failure in the Post-COVID-19 Clinic, Primary Care and Hospital Setting Using a Digital Stethoscope with AI ECG

DESIGN Prospective cross-sectional study

AIMS

1. To validate detection of left ventricular ejection fraction (LVEF) above or below 40% using single-lead ECG interpreted by machine learning algorithm (DUO-EF) compared to gold-standard investigations for calculating LVEF (echocardiography [echo], and a subgroup in cardiac MRI [cMRI])
2. To conduct a real-world evaluation of DUO-EF detection of LVEF above or below 40% in the primary care and COVID-19 follow up clinic setting; validated against subsequent gold standard investigations
3. To evaluate the positive and negative-predictive value of DUO-EF at 24 months

Methods

1. Head-to-head comparison of DUO-EF against gold standard investigation (echo and cMRI) for classifying LVEF<40%; in unselected patients attending for routine echocardiography (main study group) and cardiac MRI (subgroup) as part of their routine clinical care
2. Point-of-care DUO-EF in patients where GP suspects new heart failure and comparison with:
 - a. Subsequent DUO-EF at time of gold-standard investigation (if indicated as standard of care)
 - b. Ejection fraction as calculated by gold-standard investigation
3. Point-of-care DUO-EF in patients attending COVID-19 follow up clinic where clinician suspects new heart failure and comparison with:
 - a. Subsequent DUO-EF at time of gold-standard investigation for HF
 - b. Ejection fraction as calculated by gold-standard investigation

Telephone call follow-up at 24 months for all patients with DUO-EF suggestive of HFrEF but normal gold standard investigations

**OUTCOME
MEASURES**

- **1.) Primary: Sensitivity and specificity of DUO-EF for detecting LVEF above or below 40%**
- 2.) Secondary:
 - DUO-EF performance against subgroup LVEF calculated by cardiac MRI
 - Consistency of DUO-EF result at point-of-care in GP practice ('real world' use where GP suspects new heart failure) against repeat DUO-EF at time of gold-standard investigation
 - Consistency of DUO-EF result at point-of-care in Covid-19 follow up clinic ('real world' use where clinician suspects new heart failure) against repeat DUO-EF at time of gold-standard investigation
 - Development of LVEF <40% at 24 months in participants with initial DUO-EF suggestive of LVEF <40% but gold standard investigations LVEF >40% i.e., can DUO-EF predict future development of LVEF <40%
 - DUO-EF point-of-care determination of LVEF<40% in comparison with the components of the established NICE pathway (BNP result)

POPULATION

- **Group 1:** All-comers to **echocardiography** and cardiac MRI departments across Imperial College Healthcare NHS Trust (**echo n = 1,500**, cMRI n = 100)
- **Group 2:** Patients seen in primary care (GP) with symptoms newly suggestive of heart failure (n = 400); contributing to Group 1 if standard of care indicates need for referral to echo/cMRI
- **Group 3:** Patients seen in the COVID-19 follow-up clinic with symptoms newly suggestive of heart failure (n = 400); contributing to Group 1 if standard of care indicates need for referral to echo/cMRI

ELIGIBILITY

Inclusion criteria for all	
 - Age 18 years or above - Able to give informed consent 		
	Group 1	Group 2	Group 3
Additional inclusion criteria	
 - Patient attending for departmental echo or cardiac MRI 	
 - Attending for GP appointment; GP concerned about heart failure diagnosis and initiates patient onto routine NICE pathway 	
 - Attending COVID-19 follow-up clinic; clinician concerned about heart failure diagnosis and initiates patient onto routine NICE pathway

Exclusion criteria	Any chest wound, skin pathology or other feature that would prohibit routine stethoscope examination
---------------------------	--

DURATION Start date 01/02/2021, duration 36 months

[figure not shown]
STUDY WORKFLOW SUMMARY DIAGRAM ON NEXT PAGE

DUO-EF-19: Diagnosis of Heart Failure in the Post-COVID-19 Clinic, Primary Care and Hospital Setting Using a Digital Stethoscope with AI ECG

Study Workflow

[figure not shown]
Imperial NHS Trust Echocardiography and Cardiac MRI Departments

St Mary's, Hammersmith & Charing Cross Hospitals and Community Cardiology Centres

[figure not shown]
GP Practices

NIHR North West London Clinical Research Network portfolio support

COVID-19 Clinic

All-comers to COVID-19 follow up clinic at St Mary's Hospital

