2. STUDY OBJECTIVES

Primary objective:

1. **To test if the DUO-EF algorithm can achieve a sensitivity and specificity above 80% for detection of LVEF above or below 40% in comparison to gold-standard echocardiography**

Secondary Objectives:

- To perform a subgroup analysis of DUO-EF against LVEF calculated by cardiac MRI (another gold standard investigation for calculating LVEF <40%)
- To validate consistency of DUO-EF result at point-of-care in GP practice ('real world' use where GP suspects new heart failure) against repeat DUO-EF at time of gold-standard investigation
- To validate consistency of DUO-EF result at point-of-care in Covid-19 follow up clinic ('real world' use where clinicians suspect new heart failure) against repeat DUO-EF at time of gold-standard investigation
- To measure if participants with DUO-EF suggestive of LVEF <40% but with gold standard investigations where LVEF >40% are at increased risk of developing heart failure at 24 months i.e. can DUO-EF predict future development of LVEF <40% at 24 months
- To evaluate DUO-EF point-of-care determination of LVEF<40% in comparison with the components of the established NICE primary care pathway (e.g. BNP result)

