Protocol Allowances: Although we require 466 patients with EF >40% and 466 patients with EF <40% we have rounded these up to 500 patients. Furthermore, we will likely need to recruit up to 1,500 patients in total since it is unlikely that the first 1,000 patients will fulfil the exact breakdown of required LVEF above and below 40%.

Controls: The ‘control’ population in this study are participants with LVEF>40%. Indications for referral to echocardiography are broad and include but are not limited to: suspected or known

ischaemic heart disease, suspected cardiomyopathy, pericardial disease, murmurs, assessment of valve disease, assessment of prosthetic valves, assessing chronic lung disease, neurological disease (stroke or transient ischaemic attack), arrhythmia (palpitations and/or loss of consciousness), high blood pressure (common) and as a standard investigation considered before surgery. Many of these referred patients are found to have no abnormalities on echo and are otherwise healthy. Therefore, the unselected approach of this study to include all-comers to echo will generate a population sample that can be evaluated for alignment with the type of population in whom a screening programme for heart failure may be beneficial.

Performance characteristics: Eko Health (the 'manufacturer' of the algorithm) indicate a performance of 80% sensitivity and 80% specificity for the identification of LVEF above or below 40%

Confounders: our study design precludes confounders

Avoidance of bias for primary objective

To avoid any biases in both the recording of DUO-EF readings by the member of the research team and this influencing calculation of %LVEF by the echocardiography team (sonographer), the following steps will be taken:

- The member of the research team approaching patients in the echo department for consent will not be aware of the indication for referral at time-of-consent
- DUO-EF readings can happen before or after the echo, with the member of the research team unaware of the echo-derived %LVEF until they check the electronic health record (after DUO-EF has already been recorded).
- The sonographer will not be made aware of the results of DUO-EF, therefore not biasing any interpretation of %LVEF if borderline around 40%

Study Participant Population

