All study participants will be approached to take part and have a DUO-EF reading during the course of their routine care (minimal disruption) in the echo or cardiac MRI setting, during their GP appointment, or while attending COVID-19 follow up clinic. This will result in a large, representative study population to meet the objectives of testing the hypothesis for DUO-EF as a screening tool.

Group 1: Departmental Echocardiography and Cardiac MRI, Imperial College Healthcare NHS Trust

Unselected patients attending for departmental echocardiography (n = 1,500) and subgroup in cardiac MRI (n = 100). Patients will be consented by a member of the research team while they wait for an echocardiogram/cMRI. Patients from group 2 (GP referrals) will also be attending for an echo as part of their routine care on the heart failure pathway; they will be re-consented by a member of the research team upon arrival in the department.

Researchers will perform and record DUO-EF readings on participants and subsequently review echocardiography and cardiac MRI reports and document the LVEF calculated by these modalities.

If echocardiography does not suggest heart failure with LVEF<40% but DUO-EF does, patients will be followed-up with a **24 month phone call** (early evidence indicates the algorithm can identify low ejection fraction before being detectable on echo⁸).

Group 2: Patients in Primary care ('real world' evaluation)

NIHR North West London Primary Care **Clinical Research Network** (n = 10 GP practices). Patients attending GP with signs/symptoms of heart failure (n = 400 in total across all sites) will proceed with standard-of-care NICE heart failure pathway, with no change to standard of care through participation in study. GP's will be asked to record DUO-EF in any patient where heart failure is suspected.

Researchers will capture the point-of-care DUO-EF prediction from the GP:

- Comparing this to repeat DUO-EF ('agreement' between two time points) at time of (group 1) echocardiography (if indicated by standard of care investigations: BNP and 12-lead ECG)
- And comparing both of these DUO-EF measurements to echocardiography derived LVEF

Group 3: COVID-19 Clinic, Imperial College Healthcare NHS Trust

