3.1 STUDY OUTCOME MEASURES

The study will end after 36 months or at the point where the predetermined number of participants have been recruited; and 24-month follow up phone call has been completed for those with DUO-EF suggestive of LVEF<40% but gold-standard LVEF >40%.

Primary outcome measure:

- **Sensitivity, specificity for DUO-EF detecting LVEF above or below 40%**

Secondary outcome measures:

- DUO-EF performance against subgroup %LVEF calculated by cardiac MRI
- Consistency of DUO-EF result at point-of-care in GP practice ('real world' use where GP suspects new heart failure) against repeat DUO-EF at time of gold-standard investigation; similarly with patients attending Covid-19 follow up clinic with symptoms of LVEF <40%
- Development of LVEF <40% at 24 months in participants with initial DUO-EF suggestive of LVEF <40% but gold standard investigations LVEF >40% i.e. can DUO-EF predict future development of LVEF <40%
- DUO-EF point-of-care determination of LVEF<40% in comparison with the components of the established NICE pathway (BNP result)

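### Aim 3 promises a 24-month negative predictive value, but no DUO-EF-negative participant has a planned 24-month outcome and no LVEF is scheduled then

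*Protocol*

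**What the plan says.** **What is to be learned at 24 months**

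- Study Summary, Aims, item 3: "To evaluate the positive and negative-predictive value of DUO-EF at 24 months".
- Section 2, Secondary Objectives: whether participants with a positive DUO-EF but gold-standard LVEF above 40% "are at increased risk of developing heart failure at 24 months", restated as "can DUO-EF predict future development of LVEF <40% at 24 months".
- Study Summary, Outcome Measures, and section 3.1: the outcome is new LVEF below 40% in that same discordant group, again framed as a question of prediction.
- Section 6, follow-up table: the call is meant to show whether a positive DUO-EF signals future risk.

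**Who is followed, and how**

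- Study Summary, Methods: "Telephone call follow-up at 24 months for all patients with DUO-EF suggestive of HFrEF but normal gold standard investigations".
- Section 3, Group 1: "If echocardiography does not suggest heart failure with LVEF<40% but DUO-EF does, patients will be followed-up with a" 24-month phone call.
- Section 3.1: the study ends once recruitment is complete and the "24-month follow up phone call has been completed for those with DUO-EF suggestive of LVEF<40% but gold-standard LVEF >40"%.
- The section 6 table and Appendix 1 give the same rule for all three groups. The call is the only 24-month entry in Appendix 1.
- Section 6: the NHS Spine check of vital status covers only those due a call.
- Section 7: the list of health-record data includes echo and cardiac MRI LVEF where available, but sets no 24-month time point and names no 24-month outcome.

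**The concern.** A negative predictive value is calculated among test-negatives, and a claim of raised risk needs a comparator. The protocol follows no test-negatives, so it has neither. The outcome itself is an LVEF threshold, yet the only planned procedure is a phone call, which cannot measure LVEF.

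The danger lies in how the result would be read. Section 3 (Group 1) raises the idea that the algorithm may detect disease before echo does. Some conversions among the called patients would look like support for that. But people referred for echo have their own background rate of developing low LVEF, and this design never measures it.

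**Working it through.** **Inputs**

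- Minimum echo recruitment: 500 with LVEF above 40% and 500 below (section 3, Sample Size Calculation).
- Larger scenario: "we will likely need to recruit up to 1,500 patients in total" (section 3, Protocol Allowances). The split is not given; I take 750/750, and 1,000 above with 500 below.
- Sensitivity and specificity: 80% (manufacturer's figure and null value) to 85% (planning value), both in section 3. I assume these apply to the participant-level result.

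The protocol gives no sample size, event count or precision for the 24-month aim, so there is no stated figure to reproduce. The primary calculation does reproduce: an exact binomial test of 80% against 85%, two-sided 5%, first reaches 80% power at n = 466.

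**Step 1. Who has a planned 24-month outcome**

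Called = n(above 40%) × (1 − specificity). DUO-EF-negative = n(above 40%) × specificity + n(below 40%) × (1 − sensitivity).

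| Above / below 40% | Sens = spec | Called | DUO-EF-negative, not called |
|---|---|---|---|
| 500 / 500 | 80% | 500 × 0.20 = 100 | 400 + 100 = 500 |
| 500 / 500 | 85% | 500 × 0.15 = 75 | 425 + 75 = 500 |
| 750 / 750 | 80% | 150 | 600 + 150 = 750 |
| 750 / 750 | 85% | 112.5 | 637.5 + 112.5 = 750 |
| 1,000 / 500 | 80% | 200 | 800 + 100 = 900 |
| 1,000 / 500 | 85% | 150 | 850 + 75 = 925 |

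At 500/500 the 400-425 baseline true positives are not followed either. In all, 1,000 − 100 = 900 to 1,000 − 75 = 925 have no planned 24-month outcome.

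**Step 2. Which quantities can be estimated**

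- *Negative predictive value at 24 months*: the whole denominator is unobserved.
- *Relative risk*: the risk in DUO-EF-negatives is unobserved. If 10% of called patients converted, an assumed rate of 1%, 2%, 5% or 10% among DUO-EF-negatives with baseline LVEF above 40% would mean a relative risk of 10, 5, 2 or 1. The planned data cannot separate these.
- *Positive predictive value at 24 months*: incomplete, because baseline true positives are not followed. It can be built only if baseline LVEF below 40% counts permanently as a positive, which the protocol does not say.
- *Conversion proportion in the called group*: the right people are contacted, but no LVEF is scheduled.

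**Step 3. What the called group alone can show, if everyone is reached and LVEF is known**

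Exact (Clopper-Pearson) 95% limits:

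- 0 of 100: upper limit 1 − 0.025^(1/100) = 3.6%.
- 0 of 75: upper limit 1 − 0.025^(1/75) = 4.8%.
- 10 of 100: 4.9% to 17.6%.

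A rate near zero would argue against useful prediction. A rate around 10% cannot be interpreted without a background rate.

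**Step 4. What a comparison could show if DUO-EF-negatives with baseline LVEF above 40% were followed**

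Two-proportion z-test, pooled variance under the null, two-sided 5%. The rates are assumptions.

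| Positive v negative | 10% v 5% | 15% v 5% |
|---|---|---|
| 75 v 425 | 42% power | 82% power |
| 100 v 400 | 47% power | 88% power |

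**The case against.** Five points can be made on the other side.

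- **Negative predictive value appears only in the summary's Aim 3**, not in section 2 or 3.1. That is true, and it makes the repair easy. But section 2 still asks about raised risk with no comparator, so the problem is more than one line.
- **Records could supply the outcomes.** Section 7 captures LVEF from the health record where available, and its Missing Data paragraph expects shared records to make most missing data retrievable. This shows a feasible route, not a plan: neither text sets a 24-month time point or outcome, and the second concerns missing data. An analysis plan cannot by itself create outcomes that the protocol does not collect.
- **Heart failure is a diagnosis that a call plus records could establish.** This is fair for the first half of the section 2 objective. The second half and the outcome measures in section 3.1 specify LVEF.
- **The count of 900-925 overstates the gap.** If the outcome were LVEF below 40% at any time up to 24 months, the 500 with low baseline LVEF would already be classified, and the gap would be the 400-425 true negatives. That is correct under that definition, but the protocol does not adopt it.
- **The 75-100 called is not a bound.** Section 3 assumes at least 85%, so fewer is possible. It also calls a participant positive if any of five readings is positive. If 80-85% were per-reading specificity and readings were independent (both assumptions), 1 − 0.85^5 = 56% to 1 − 0.80^5 = 67% of those with LVEF above 40% would be called, about 278-336 of 500. Groups 2 and 3 would also add calls. The counts are therefore illustrative, but whatever they are, no DUO-EF-negative is followed.

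**Conclusion.** The concern holds. The protocol fixes who is followed and how, and under that rule the 24-month negative predictive value and any relative risk cannot be estimated. This conclusion is structural and does not depend on the assumed accuracy. The sizes do: they rest on participant-level sensitivity and specificity of 80-85% in echo patients and on complete contact. The outcome measure in section 3.1 matches the people called but lacks a planned source of LVEF. The cross-sectional primary objective and its sample size are not affected. This should be fixed, but it does not threaten the main result.

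**What to change.** Choose one of two routes.

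**Minimum: narrow the claim.**

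- Remove the negative predictive value from Aim 3.
- Remove the risk and prediction wording from the Study Summary outcome measures and sections 2, 3.1 and 6.
- Report a descriptive rate of clinically detected LVEF below 40% among the called patients, with the share who were re-imaged.
- Keep a 24-month positive predictive value only if it is defined as LVEF below 40% at any time up to 24 months.

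This costs wording only; the prediction question is given up.

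**If the prediction question is kept: follow both groups alike.**

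- For every participant with baseline gold-standard LVEF above 40%, DUO-EF positive or negative, extract later echo or cardiac MRI LVEF, heart failure diagnosis and death from existing records.
- Use the same window and method in both groups, with the extractor blind to DUO-EF.
- Define the outcome as record-detected LVEF below 40% at any time up to 24 months, and report the share re-imaged in each group.
- Leave phone data, which exist only for positives, out of the comparison.
- If a negative predictive value is reported, count baseline false negatives as events. With 500/500 it then cannot exceed 400/500 = 80% to 425/500 = 85% before any conversion, so it would largely restate baseline accuracy. The conversion rates by DUO-EF result are the more useful comparison.

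This costs an amendment, a consent check and a further records query. Only clinically detected disease is captured, re-imaging may differ between the groups, and power is modest for a doubling of risk (42-47% for an assumed 10% v 5%).

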1. INTRODUCTION

1.1 BACKGROUND

Heart Failure

One million people in the UK are living with heart failure (HF), with more than 60,000 new cases annually. Consuming 2% of the entire NHS budget, HF has a worse prognosis — 50% mortality within five years — than most cancers. Furthermore, hospital admissions and demand for social care related to HF is expected to increase by 50% by 2040.¹ Given this massively increasing prevalence of HF, the evidence for the benefits of early diagnosis and treatment coupled with the importance of accuracy and difficulty in diagnosis, HF is one of the biggest challenges facing the NHS, for which better, early diagnostic and management strategies are urgently needed.

HF is a clinical syndrome with a wide spectrum. The majority of patients with HF have heart failure with reduced ejection fraction (HFrEF), characterised by a reduction in blood pumped out of the left ventricle with each heartbeat, as seen on an echocardiogram (an ultrasound-based medical imaging tool, where above 50% is considered normal ejection fraction). **HFrEF is defined as a left ventricular ejection fraction (LVEF) below 40%.** The clinical syndrome of heart failure with preserved ejection fraction (HFpEF) features similar clinical symptoms (e.g. breathlessness, fatigue, ankle swelling) to HFrEF. However, it is difficult to diagnose and no treatment has been proven in pivotal clinical trials to be effective for HFpEF,² the mortality from which is lower than treated HFrEF, even when optimally managed.

There is strong and abundant evidence that early effective drug therapy can improve symptoms and prognosis in patients with HFrEF (LVEF <40%), where a substantial portion of increased morbidity and mortality is attributable to late initiation of therapies — caused by delayed diagnosis.³

HF is poorly served in primary care, as it can be difficult to diagnose from non-specific symptoms. Delays in diagnosis lead to late initiation of life-prolonging therapies. Current clinical management guidelines from the National Institute for Health and Care Excellence (NICE) suggest performing a brain natriuretic peptide blood test (BNP) when HF is suspected. According to the NICE guidelines, if BNP is elevated, the GP makes a referral for specialist tests (echocardiogram) and assessments within six weeks - two weeks if BNP is especially high.¹

Only 4% of patients complete these NICE-recommended investigations in the recommended time frame,³ largely reflecting this unwieldy diagnostic pathway, limited resources, and HF being a common condition that is inherently difficult to diagnose.

Consequently, although 40% of patients might previously have seen their GP with HF symptoms (including breathlessness, ankle swelling, fatigue), the diagnosis of HF is made in 80% of cases

when patients have advanced, severe (and life-threatening) worsening of symptoms, requiring hospital admission.⁴ HF is now the most common reason for acute hospital admission in those aged over 65 and improving diagnosis in the community is listed as an explicit priority for the NHS Long Term plan.⁵

Heart Failure and COVID-19

It is now indisputable that patients with COVID-19 are at increased risk of cardiovascular complications, in many cases culminating in heart failure.⁶ As our understanding continues to develop, some studies have suggested myocardial involvement is present in as many as 78% of patients.⁷ Importantly, a substantial proportion of heart failure in need of treatment to prolong life is initially asymptomatic. Guidance from the British Thoracic Society⁸ recommends all patients who attended hospital with clinico-radiological findings of COVID-19 should be followed up as an outpatient within six weeks -- a huge challenge given the high volume of patients.

Part of this care involves measurement of blood oxygen saturations and testing to screen for chronic lung disease. At present, despite the known cardiovascular complications, no routine screening for heart failure is being done for patients in this setting. This is partly due to the gold standard diagnostic for heart failure -- echocardiography -- being a limited, expensive and specialist resource.⁹

Eko DUO Digital Stethoscope with Artificial Intelligence Electrocardiogram (ECG)

The Eko DUO, is a stethoscope with an expanded acoustic “bell” with which heart sounds can be heard either through conventional rubber tubing (removable) with conventional ear pieces or via a connected mobile phone speaker. Eko DUO is also unique among stethoscopes in featuring a single-lead electrocardiogram (ECG). The Eko DUO and ECG capability are fully CE marked.

With just 15 seconds of Eko DUO ECG data, a deep neural network (a form of artificial intelligence), developed at the Mayo Clinic in the US, can accurately **predict low ejection fraction, abbreviated for this study as DUO-EF**. Previous studies (n = 100) have shown DUO-EF has high accuracy for achieving this (AUC 0.906 [CI: 0.831-0.955] for EF <=35%; 0.841 [CI: 0.754 - 0.906] for EF<50%).¹⁰

Single-lead ECG requires only two contact points, as in the case of the two stainless steel electrodes on the body of the Eko DUO device, touched to the skin of the patient's chest wall for instantaneous acquisition of ECG signal. Single-lead ECG is already well established to be

adequate for a machine learning algorithm that detects atrial fibrillation, now a standard feature of some of the biggest consumer wearable technologies (e.g. Apple Watch Series 4). The Eko DUO is able to give a DUO-EF reading at the clinically significant threshold of 40% using single-lead ECG alone -- a study of 100 patients at the Mayo Clinic showed an AUC of 0.89 for detection of LVEF above or below 40%.¹¹

Eko DUO Device Regulatory Approvals

The Eko DUO device with ECG has full Conformite European (CE) marking. This study will seek approval both from the Health Research Authority research ethics committee for use of the **DUO-EF algorithm as a ‘medical device’**..

In the US, the Food and Drug Administration (FDA) has cleared Eko DUO and its AI-algorithms for heart sound interpretation and ECG detection of atrial fibrillation. The algorithm for detecting low EF recently received FDA Breakthrough Status and fast-track approval in the US. The 12-lead ECG algorithm has recently (May 2020) received Emergency Use Authorization for use during the COVID-19 pandemic.

